### **5.2.11 Cardiovascular measures**

An ECG will be obtained at screening to determine suitability for QT measurements. If the initial QTc value is prolonged, the ECG should be repeated two more times (with 5 minutes between ECG readings) and the average of the 3 QTc values used to determine eligibility.

### **5.2.12 Actigraphy measures**

An actigraph to remotely monitor sleep-wake cycles will be administered to eligible participants to wear continuously until the day after the experimental visit. This is a non-invasive wrist-worn device that captures movement.

## **5.3 Enrolment procedures**

Participants who are eligible at screening will be invited to attend the experimental study visit and upon confirmation of attendance will undergo enrolment and randomisation.

### **5.3.1 Anonymisation and randomisation**

Each participant will be given a unique participant identification number upon entering the study which will not change.

The randomisation to either baclofen or placebo (3:1 ratio) will be performed using the online software application, Sealed Envelope TM.

Then the participant's current prescribed dose of methadone will be entered into the Bayesian adaptive model which, in conjunction with previous DLT toxicity data, will

recommend the baclofen dose to be assigned as either 10, 30, 60 or 90mg baclofen. As previously stated, this recommendation can be over-ridden based on cumulative clinical experience. The adaptive Bayesian model will be programmed into R. A custom-built OpenClinica Clinical Data Management and Electronic Data Capture software database, will store the output of the randomisation and baclofen dose where relevant.

After randomisation, if a participant does not attend the experimental visit within the expected time window, the research team will have the option to replace this individual with a new participant, as appropriate. The new participant would receive the same allocation of placebo or baclofen, but if allocated to baclofen the allocated dose might change, depending on the methadone dose-level and recommendation of the adaptive model at that point in time. This would not exclude the replaced participant from re-entering the study at a later date, at which point they would be re-randomised.

After randomisation, all paper and electronic case report forms will utilise the participant study ID number, rather than personal identifiers wherever possible.

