### **5.7.4 Emergency Unblinding Procedure**

This is single-blind- study clinicians and researchers will be aware of the drug allocation that was recommended by the adaptive trial algorithm and this allocation will be stored within the OpenClinica Database and accessible to the research team.

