## **5.8 Study Durations**

### **5.8.1 Protocol in event of experimental day failure**

In the event that a participant does not attend as planned, or tests positive for alcohol or drugs of abuse, or is ineligible for the study day (e.g. positive covid test, illness) prior to baclofen administration, the experimental visit will be re-scheduled. The participant would retain their baclofen or placebo randomisation, and their baclofen dose allocation. However, depending on the length of time between the cancelled and re-scheduled visit, and the potential for updates to the adaptive model in the intervening time, the baclofen dose level may be re-allocated, according to the discretion of the Dose Setting Committee.

In the event that a participant has been administered medication during an experimental study visit, and there is subsequently a problem (e.g. fire alarm, non-recoverable equipment malfunction), that results in significant data loss such that the participant does not meet criteria for an evaluable participant, with the continued consent of the patient the study day (including drug administration) will be repeated at another scheduled session (in at least 5 days' time if participant was randomised to baclofen).

In the event that a participant does not re-schedule and is considered 'lost', that participant can be replaced if required (i.e. to make total of 48 on baclofen if safety has not yet been established). The replacement participant should receive the same treatment (placebo or baclofen) of the participant that is being replaced. However, in this case, the baclofen dose level may be re-allocated, as informed by the current model based on the replacement person's own methadone dose, and at the discretion of the Dose Setting Committee.

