## **6.2 Number of Participants**

The sample size is not fixed. Up to a total of 64 patients are planned to be enrolled in the study with up to 48 patients on the experimental doses and up to 16 on placebo, as recommended by the trial algorithm in consultation with clinicians and the study team.

The drop-out rate from the study is estimated to be approximately 20% following screening. We therefore anticipate screening up to 100 methadone-maintained opioid dependent participants for entry into the study, with ~75% eligibility rate at screening, and a further ~20% drop out prior to, or at the experimental session.

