### **8.2 METHODS OF RANDOMISATION**

The randomisation schedule will be generated by Sealed Envelope, or independent statistician, using a 3:1 ratio (baclofen: placebo). Blocked randomisation will be used to maintain the 3:1 ratio throughout the study.

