### **8.2 SAMPLE SIZE**

The sample size in Phase I is not fixed. Up to a total of 64 patients are planned to be enrolled in the study with up to 48 patients on the experimental baclofen doses and 16 on placebo with a 3:1 allocation ratio. The final sample size will depend on the escalation/de-escalation decisions made using the trial and on the recommendation of the model on stopping earlier. The performance of the Bayesian design based on 48 participants was assessed via simulations under several clinically relevant scenarios in terms of accuracy of the number of patients that would receive (i) their individual target dose combination and (ii) a combination that is safe for them in the subsequently planned phase 2 trial.

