### **9 DATA AND STUDY MANAGEMENT**

#### **9.1 Data Monitoring & Interim Analyses**

A DMC will be convened and meet regularly to discuss study progress, recruitment targets and future planning. If a trial stopping rule was triggered a DMC meeting would be convened to review the TMG's decision to stop/continue the trial.

Quality control checking and introduction of improvement procedures for data analysis will be ongoing throughout data collection. The study uses the continual reassessment method to assess the dose-toxicity response. There is no formal plan for interim data analysis of secondary outcomes before the completion of the study, however data will be continuously monitored to determine whether data collection should continue as planned, or be targeted towards a particular demographic or methadone dose to increase precision in secondary outcomes.

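### A replacement takes the arm of the person replaced, which staff already know, so those places in the placebo comparison are neither randomised nor concealed

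*Combined protocol and SAP*

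**What the plan says.** Section 5.3 places randomisation between screening and the experimental visit, once the participant has confirmed attendance. On method, section 8.2 says: "Blocked randomisation will be used to maintain the 3:1 ratio throughout the study". No block size is given. The trial is single-blind. Section 5.7.4 states that "study clinicians and researchers will be aware of the drug allocation that was recommended by the adaptive trial algorithm", and adds that the research team can see the allocation in the database.

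Two sections deal with a participant who has been randomised but is not dosed as planned.

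- **Section 5.3.1.** Non-attendance within the expected window gives the team an option to replace the person. "The new participant would receive the same allocation of placebo or baclofen, but if allocated to baclofen the allocated dose might change". Of the person replaced it says: "This would not exclude the replaced participant from re-entering the study at a later date, at which point they would be re-randomised".
- **Section 5.8.1.** After non-attendance, a positive drug or alcohol test, or ineligibility on the day, the visit is re-scheduled. "The participant would retain their baclofen or placebo randomisation, and their baclofen dose allocation", although the dose may be revisited. Someone who does not re-schedule and is considered lost can be replaced, and the replacement again takes the same treatment.

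Neither section says that the replacement is identified by someone unaware of the arm. Neither gives a time limit or other fixed criterion for being lost.

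**The concern.** Section 2.10 includes the placebo arm to evaluate pharmacodynamic effects and to control for expectation. The secondary objectives (3.1.2) and outcomes (3.4.4) read sub-threshold respiratory change, T-SHAS and DEQ against placebo, and the findings are to inform the next trial. That reading depends on the two groups differing only by chance apart from treatment.

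A replacement breaks this condition, because the arm is settled and known to the team before the person is enrolled. The plan also lets recruitment be steered: under section 9.1, data collection may "be targeted towards a particular demographic or methadone dose to increase precision in secondary outcomes". Steering does no harm while the next allocation is unknown. Once the arm is known, it can make methadone dose, sex or general health differ between arms.

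The planned analysis offers little protection. Section 8.3.3 is mainly descriptive, and the mixed models that could include methadone dose are optional. No adjustment deals with unmeasured selection. With at most 16 on placebo, a few selected people can shift a mean.

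**Working it through.** **Inputs from the documents.** Section 8.2 plans "up to 48 patients on the experimental baclofen doses and 16 on placebo with a 3:1 allocation ratio". Section 6.2 expects "a further ~20% drop out prior to, or at the experimental session". The documents do not give the share of that loss that falls after randomisation, or how often the replacement option would be used.

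**The plan's own figure.** 64 × 3/4 = 48 and 64 × 1/4 = 16, so the stated split is reproduced. Section 8.1 states that there is no formal testing and no power calculation, so there is nothing further to reproduce.

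**How many places could be affected.** Let d be the proportion lost after randomisation, with every loss replaced. The expected number of places whose first holder is lost is N × d. The number of replacements needed to dose 64 is 64/(1 − d), rounded up, minus 64. The chance that at least one placebo place is affected is 1 − (1 − d)^16. The values of d are assumptions. The largest takes all the loss in section 6.2 as falling after randomisation.

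| d | Replacements | Places of 64 | Baclofen of 48 | Placebo of 16 | Chance of at least 1 placebo place |
|---|---|---|---|---|---|
| 5% | 4 | 3.2 | 2.4 | 0.8 | 56% |
| 10% | 8 | 6.4 | 4.8 | 1.6 | 81% |
| 20% | 16 | 12.8 | 9.6 | 3.2 | 97% |

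Section 4.4.2 gives minimum numbers of 3 + 3 + 12 + 12 = 30 on baclofen and 10 on placebo. On these, the placebo places affected would be 0.5, 1.0 and 2.0.

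**The two routes side by side.** In 5.8.1, non-attendance leads to re-scheduling with the arm kept, and replacement follows only for someone considered lost. In 5.3.1, non-attendance within the window is enough to open replacement, with no mention of being lost, and a replaced person who returns is drawn again. One event can therefore end in a kept arm or in a new draw with a 75% chance of baclofen. Staff who know the first arm choose the route.

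**Is copying the arm needed to hold 3:1?** A simulation of 20,000 runs gave each newcomer the next allocation on the list and recruited until 64 were dosed. It assumed blocks of 4 and loss independent of arm. The mean placebo count stayed at 16.0. The central 95% range was 14 to 17 at 5% loss, 14 to 18 at 10% and 13 to 19 at 20%. The ratio is held closely enough without the same-arm rule.

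**The case against.** A reader might infer more than the documents support, and most of the case on the other side is an answer to those stronger readings.

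- **That 5.3.1 and 5.8.1 contradict each other.** They can be read in sequence: re-schedule first, replace if lost, draw again only if a replaced person comes back. What stands is that no fixed criterion separates the steps.
- **That a person randomised twice biases an intention-to-treat comparison.** The full analysis set (8.3.1.1) is used only for conduct and disposition. The outcome sets (8.3.1.2 and 8.3.1.3) require that study drug was received, and a non-attender was not dosed the first time. At most this is an ambiguity in the disposition table.
- **That 13 of 64 places is the expected number.** The 20% in section 6.2 counts loss after screening, and some of it precedes randomisation. Replacement is optional, participants who fail on the day are re-scheduled, and 64 is a maximum. The purpose stated in 5.8.1 is reaching 48 on baclofen. The same-arm rule names placebo too, but no reason for replacing placebo participants is given.
- **That staff pick people for a known arm.** The targeting sentence in 9.1 concerns data collection overall and mentions neither replacements nor arms. The valid point is that nothing in the plan prevents such a choice.
- **That the primary result is compromised.** Section 8.3.2 models DLT risk on the baclofen and methadone doses, and the model and the Dose Setting Committee set the dose for each participant's methadone level. Section 8.1 calls all analyses exploratory.

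These points limit the size and reach of the problem. They do not restore randomisation or concealment for the replaced places.

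**Conclusion.** The point holds in a limited form. Each replacement place is filled by someone whose arm is fixed and visible to the team before enrolment. The choice between keeping an arm and drawing a new one rests with open staff and has no fixed rule. The harm is confined to the exploratory contrasts with placebo and does not materially reach the dose-toxicity model.

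The counts in the table are upper values at each loss rate, because they assume that every loss is replaced. The 20% row is an upper bound on the loss as well. Even at 5%, with all losses replaced, it is more likely than not that at least one of 16 placebo places would be affected. The correction is cheap and should be made.

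**What to change.** 1. In 5.3.1 and 5.8.1, replace the same-arm rule with one under which every replacement receives the next concealed allocation from an extended Sealed Envelope list. Apply it also to replacements for participants who were dosed but are not evaluable (3.4.7, 5.8.1).
2. Delete the re-randomisation sentence in 5.3.1, so that a returning participant always keeps the first allocation.
3. Reconcile 5.3.1 with 5.8.1 by using one fixed criterion for when a participant is considered lost.
4. Where dispensing allows, randomise on the day, after the checks in 5.4.1. This removes most replacements. The number of tablets follows the model's recommendation in both arms (5.7), so a dose recommendation is needed before the draw in any case. Same-day randomisation must fit dispensing against a prescription (5.7.3) and the short methadone-to-baclofen interval (5.4.2). It does not cover participants who are dosed but not evaluable, so items 1 to 3 are still needed.

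**Cost.** Protocol wording and a longer list. The final ratio may drift slightly from 3:1, to about 13 to 19 on placebo of 64 at 20% loss under the assumed blocks of 4. A vacated baclofen place in a group may not be refilled at once, which groups of up to 3 permit.

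**Limit.** Open staff can predict some allocations within a block. If blocks were of 4, the allocations already made would determine on average (3 + 2 + 1 + 1)/4 = 1.75 of each 4, or 44%. The next allocation is then not fully concealed, but that is still better than an arm known with certainty.

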## **5.4 Experimental study visit procedures**

Experimental study visits will take place at the NIHR Imperial Clinical Research Facility (CRF) at Hammersmith hospital, lasting approximately 6-7 hours (with breaks). This follows previous protocols which have been acceptable and well tolerated by participants. At each study visit participants will take their usual dose of methadone, undergo baseline assessments and receive a single dose of orally administered placebo or baclofen. Measures of safety, PK-PD, self-report questionnaires and adverse effects will be taken prior to, and at regular intervals following baclofen administration, according to section 4.3, to coincide with peak plasma concentrations, peak anticipated pharmacodynamic response and for up to 5 hours, allowing adequate rest breaks for participants.

The following assessments will take place:

### **5.4.1 Eligibility check**

Participants will arrive at the research centre and confirm consent. Transport will be arranged where appropriate. Refreshments made available throughout the day. Lunch will be provided. Smoking is permitted at regular intervals as required, to avoid nicotine withdrawal, but smoking will be avoided in the 15 minutes prior to each hourly time-point and during the first 2 hours following dosing. Caffeine intake will be permitted (according to usual consumption).

Upon arrival, eligibility will be checked and drug urine screen, alcohol breath and pregnancy tests obtained (see procedures above)

### **5.4.2 Methadone Dosing**

Participants will take their usual dose of prescribed daily methadone, and the time noted.

NB: In those receiving daily prescription methadone, given their long-term use, plasma levels will be at steady-state during the day. The vast majority of participants take their methadone in the morning, therefore on experimental visits, participants will bring their

usual methadone dose with them to the research facility, and consume it under observation on the premises, shortly after arrival. Maximal plasma levels of methadone are reached in 1.8-3.8h with half-life of ~24hrs (independent of dose, (Wolff et al., 1993). Our previous experience is that a short delay in taking methadone is acceptable to participants and we do not anticipate substantial discomfort. However, to minimise this, the methadone will be taken as early as possible, and the gap between methadone and baclofen administration will be kept short (~40-60 minutes).

#### **5.4.3 Baclofen or Placebo Dosing & Administration**

The dose recommendation from the model will be administered approximately 1 hour after methadone. The dose levels are 10mg, 30mg, 60mg or 90mg, administered as either 1, 3, 6 or 9 tablets of baclofen respectively, or a matching number of placebo (vitamin D) tablets which are a very close visual match (see section 5.7).

Effects of baclofen or placebo will be monitored for up to 5 hours following dosing at the Clinical Research Facility. Any lasting effects will be monitored at a follow-up telephone call the following day.

Placebo or baclofen tablets will be administered with water by a nurse or study team member under direct supervision. Participants will not be given the chance to scrutinise the contents of the medication pot prior to consumption. This is a single-blind trial, therefore the participants will not be aware of whether they are taking placebo or baclofen tablets.

NB Baclofen reaches peak maximum concentrations approximately 1-2 hours after oral dosing with 60mg ( $C_{max}$ ; 88-102 minutes, (Durant et al., 2018), and has an estimated half-life in plasma of ~3 hours after a single 60mg dose (range = 2.7-3h from 10-90mg baclofen). All testing will therefore be covered by baclofen's pharmacokinetic profile.

#### **5.4.4 Respiratory measures**

Following baclofen administration, continuous monitoring of the patient will occur for the first 120 minutes.

**Blood gases:** Pulse oximetry, capable of continuous recording, will be used for regular static, and periodic continuous monitoring and recording of the blood oxygen saturation whilst seated, or semi-supine.

For safety, whilst the participant is not under direct supervision but remaining in the ICRF, continuous pulse oximetry will continue to be monitored at the remote nursing station for the first 120 min following drug administration.

Capnography and/or transcutaneous  $CO_2$  measurements will be obtained at regular intervals, with periodic continuous monitoring and recording of  $ETCO_2$ /partial pressure and respiratory rate via a nasal cannula.

#### **5.4.5 Intervention measures**

Intervention levels (0 to 4) will be utilised if marked sedation occurs (see section 3.4.3).

#### **5.4.6 Sedation measures**

Glasgow Coma Scale (GCS) will be obtained at baseline (after methadone dosing), and then every hour following baclofen dosing. The GCS assesses the participant's ability to open their eyes, move and speak, and has a minimum score of 3 with a maximum of 15.

National Early Warning Score 2 (NEWS2) for clinical deterioration. It is a staff rated aggregate scoring system (not self-report), with the magnitude of the score reflecting how extremely the parameter varies from the norm. The minimum score of zero and maximum of 20 and comprises the following 6 physiological parameters:

1. Respiratory rate
2. Oxygen saturation
3. Temperature
4. Systolic blood pressure
5. Pulse rate
6. Level of consciousness or new confusion (ACVPU; alert, confusion, voice, pain, unresponsive) score

#### **5.4.7 ECG measures**

An ECG to measure possible QT prolongation will be obtained at 3 timepoints; baseline (after methadone dosing), after anticipated peak effects ( $t=120\text{min}$ ) and prior to discharge (approx. 5-6h post-dose). If the initial QTc value is prolonged, the ECG should be repeated two more times (with 5 minutes between ECG readings) and the average of the 3 QTc values taken.

#### **5.4.8 Vital Signs**

Under direct observation, heart rate will be measured at regular static time points whilst seated, or semi-supine. For safety, whilst the participant is not under direct supervision but remaining in the ICRF, continuous pulse oximetry will monitor heart rate at the remote nursing station.

Blood pressure will be measured via a cuff at before and after methadone dosing, and at regular static time points whilst seated, or semi-supine, every hour following drug administration dosing.

Body Temperature will be monitored as part of the MEWS score, using an aural thermometer.

#### **5.4.9 Visual analogue scales**

Visual analogue scales (VAS) will be used to assess mood and drug effects including drug liking, anxiety and craving which will be assessed before and after baclofen administration at regular time points throughout the study day – these will allow us to document the known central effects of baclofen if any.

##### **5.4.8.1 Drug effects (general) scales**

Subjective High Assessment Scale (SHAS) will be obtained at baseline, before and after methadone dosing, and every hour following baclofen dosing.

#### **5.4.8.2 Drug effects & Liking scale**

Drug Effects Questionnaire (DEQ; feel, liking, dislike, high, want more)

#### **5.4.8.3 Other**

VAS for craving, anxiety

### **5.4.10 Other questionnaires**

The Clinical Opiate Withdrawal Scale (COWS, (Wesson & Ling, 2003)) will be administered at baseline, and again at 2 further time-points to check that the participant is not in overt withdrawal.

